4.5.2. Secondary Efficacy Variables

The secondary efficacy endpoints are:

- TSS, TNSS, and TOSS, averaged over the duration of the birch pollen season, in subjects who receive a single dose of REGN5713-5714-5715 versus placebo
- DMS, averaged over the duration of the birch pollen season, in subjects who receive a single dose of REGN5713-5714-5715 versus placebo
- Change and percent change from baseline to the end of study in birch SPT mean wheal diameter in subjects who receive a single dose of REGN5713-5714-5715 versus placebo
- The number of "well days" in each of the treatment groups, where the "well days" are defined as days when rescue medication is not utilized and the TSS is $\leq 2/18$

Birch Allergen and Standard Regional Skin Prick Tests

An SPT with birch allergen extract and a regional SPT (such as with dust mites, grasses, ragweed, other trees, including other birch homologous trees [such as alder and oak], mold, cat, and dog) will be performed to assess sensitization status. Skin prick test data may be used to determine the relationship between birch and regional allergen sensitization at baseline and pharmacodynamic effects of REGN5713-5714-5715 to reduce allergic symptoms upon birch pollen allergen challenges. Mean wheal diameter is measured approximately 15 minutes after placement. Aside from the birch skin test requirement for enrollment (which is >=5mm compared to the negative control), a positive response is defined by a mean wheal diameter at least 3 mm greater than a negative control.

4.5.3. Exploratory Efficacy Variables

Exploratory efficacy endpoints include:

- RQLQ (S), averaged over the duration of the birch pollen season, for REGN5713-5714- 5715 versus placebo
- ACQ-5, averaged over the duration of the birch pollen season, for REGN5713-5714-5715 versus placebo (only for patients with asthma)
- Change and percent change from baseline to the end of study in SPT mean wheal diameter for birch homologous/cross-reactive allergens in REGN5713-5714-5715 versus placebo
- Baseline allergen-specific IgE levels and correlation with average CSMS, TSS, TNSS, TOSS, DMS during birch pollen season
- Number of baseline sensitizations to other allergens (poly/mono-sensitization status, based on allergen-specific IgE levels) and correlation with CSMS, TSS, TNSS, TOSS, and DMS, averaged over the duration of the birch pollen season
- Baseline serum antibody levels and correlation with CSMS, TSS, TNSS, TOSS, and DMS, averaged over the duration of the birch pollen season

Regeneron Pharmaceuticals, Inc. Statistical Analysis Plan

- To assess the reduction in PFAS and related symptoms, as measured by PFASQ, from baseline to end of study
- To assess patient rating of severity of seasonal allergy symptoms, as measured by PGI-S, from baseline to end of study

Standardized Rhinoconjunctivitis Quality of Life Questionnaire [RQLQ (S)]

The RQLQ (S) has 28 questions in 7 domains: activity limitation, sleep problems, nose symptoms, eye symptoms, non-nose/eye symptoms, practical problems, and emotional function. There are 3 subject-specific questions in the activity domain that allow subjects to select 3 activities in which they are most limited by their rhinoconjunctivitis. Subjects recall how bothered they have been by their rhinoconjunctivitis during the previous week and respond to each question on a 7-point scale (0 [not impaired at all] to 6 [severely impaired]). The overall RQLQ (S) score is the mean of all 28 responses, and the individual domain scores are the means of the items in those domains (Juniper, 1991). The RQLQ (S) will be recorded using an e-diary.

Asthma Control Questionnaire

The ACQ measures the adequacy of asthma control and change in asthma control that occurs spontaneously or as a result of treatment. The ACQ-5 is comprised of 5, patient-reported items that were rated by clinicians as the most important to evaluate control: (1) awakening at night due to symptoms, (2) morning symptoms, (3) limitation of daily activities, (4) shortness of breath, and (5) wheezing. The total score ranges from 0 to 6 with higher scores denoting less asthma control. A score of ≥ 1.5 is considered as uncontrolled asthma. The ACQ-5 will be recorded using an e-diary for patients with asthma.

Pollen Food Allergy Symptom Questionnaire (PFASQ)

The PFASQ will be performed to determine the types of food that produce an allergic reaction, the type of reaction, and how soon the reactions occur.

Patient Global Impression of Severity (PGI-S)

The PGI-S assesses the severity of seasonal allergy symptoms over the past 1 week. Symptom severity ranges from 0 (no symptoms), 1 (mild), 2 (moderate), and 3 (severe) symptoms.

4.6. Safety Variables

4.6.1. Adverse Events and Serious Adverse Events

Adverse events (AEs) and serious adverse events (SAEs) defined in study protocol 10.2.1 and 10.2.2 will be collected from the time of informed consent signature and then at each visit until the end of the study. All adverse events are to be coded using the Medical Dictionary for Regulatory Activities (MedDRA).

Treatment-emergent adverse events (TEAEs) are defined as those that are not present at baseline or represent the exacerbation of a pre-existing condition during the on-treatment period.

4.6.2. Adverse Events of Special Interest

Adverse events of special interest (AESI) for this study include systemic or severe hypersensitivity reactions and severe injection site reactions.

4.6.3. Laboratory Safety Variables

Hematology, chemistry, pregnancy test, and urinalysis will be analyzed by a central laboratory. Samples for laboratory testing will be collected at visits according to Table 3. Tests will include:

Blood chemistry

Sodium	Total protein, serum		Total bilirubin
Potassium	Creatinine		Triglycerides
Chloride	Blood urea nitrogen (BUN	1)	Uric acid
Carbon dioxide	Aspartate aminotransferas	e (AST)	
Calcium	Alanine aminotransferase	(ALT)	
Glucose	Alkaline phosphatase		
Albumin			
Hematology			
Hemoglobin	Differe	ntial:	
Hematocrit	Ne	utrophils	
Red blood cells (RBCs)	Ly	mphocytes	
White blood cells (WBCs)	Mo	onocytes	
Red cell indices	Ba	sophils	
Platelet count	Eosinophils		
Urinalysis			
Color	Glucose		RBC
Clarity	Blood		Hyaline and other casts
pН	Bilirubin		Bacteria
Specific gravity	Leukocyte estera	se	Epithelial cells
Ketones	Nitrite		Crystals
Protein	WBC		Yeast

Other laboratory tests

Subjects will be tested for FSH levels (postmenopausal women only) and will undergo serum and urine pregnancy testing (WOCBP only); pregnancy testing is not required of women confirmed postmenopausal. If any urine pregnancy test is positive, the site must perform a serum pregnancy test for confirmation. If a serum pregnancy test must be performed, study drug cannot be administered unless the serum pregnancy test is negative.

Samples will be collected for quantitative assessment of total and allergen-specific IgE and will be analyzed by a central laboratory.

4.6.4. Vital Signs and Weight/Height

Vital signs include systolic and diastolic blood pressure, respiratory rate and heart rate. Vital signs will be collected in a seated position. On the day of study drug administration, vital signs are taken

CONFIDENTIAL

Page 29 of 35

prior to PK blood draw, prior to study drug administration, and at 2 hours (± 10 min) after completion of the injection.

Weight and height are measured at screening visit 1 only.

4.6.5. 12-Lead Electrocardiography (ECG)

A standard 12-lead ECG will be performed at the screening visit 1 only. Heart rate will be recorded from the ventricular rate and the PR, QRS, and QT intervals will be recorded. The ECG strips or reports will be retained with the source documentation.

To minimize variability, it is important that the patient be in a resting position for ≥ 10 minutes prior to the ECG evaluation. Body position should be consistently maintained for each ECG to prevent changes in heart rate.

4.6.6. Physical Examination Variables

The physical examination variable values are dichotomized to normal and abnormal.

4.6.7. Spirometry

Spirometry (American Thoracic Society [ATS]/European Respiratory Society [ERS]-compliant) as adjudicated by the site investigator, including measurements of forced vital capacity (FVC [L]), forced expiratory volume (FEV1 [L]), FEV1/FVC (%), peak expiratory flow (L/s), forced expiratory flow 25 to 75 (L/s), will be performed during screening and randomization to exclude any subjects with abnormal lung function and/or poorly controlled asthma.

4.7. Pharmacokinetic Variables

Concentrations in serum of total (free+bound to target) REGN5713, REGN5714, and REGN5715 will be determined at time points specified in the study schedule of events in Section 10.2. Pharmacokinetic variables consist of invididual antibody, as well as total drug, concentration in serum and time (both nominal and actual).

4.8. Immunogenicity Variables

The immunogenicity variables are ADA status, ADA titer, NAb status and time point/visit. Samples in this study will be collected at the clinic visits specified in Section 10.2. Samples positive in the ADA assay will be further characterized for ADA titers. Anti-REGN5713, REGN5714, and REGN5715 neutralizing antibodies (NAb) analysis may be performed on ADA-positive serum samples. The overall immunogenicity risk will be taken into consideration to assess the need for NAb analysis. Serum samples will be banked, if NAb analysis is to be conducted at a later time.

Immunogenicity will be characterized by the ADA response and titer categories observed:

ADA response category:

• ADA Negative, defined as ADA negative response in the ADA assay at all time points, regardless of any missing samples.

- Pre-existing immunoreactivity: defined as either an ADA positive response in the ADA assay at baseline with all post first dose ADA results negative, OR a positive response at baseline with all post first dose ADA responses less than 9-fold over baseline titer levels.
- Treatment-emergent ADA response: defined as a positive response in the ADA assay post first dose when baseline results are negative or missing.
- Treatment-boosted ADA response: defined as a positive response in the ADA assay post first dose that is greater than or equal to 9-fold over baseline titer levels, when baseline results are positive

Titer category (Maximum titer values)

- Low (titer <1,000)
- Moderate $(1,000 \le \text{titer} \le 10,000)$
- High (titer >10,000)

The NAb status is categorized as follows:

- Negative: Samples tested negative in the ADA assay, or samples positive in the ADA assay but tested negative in the NAb assay
- Positive: Samples positive in the NAb assay

4.9. Biomarker Variables

Exploratory biomarker variables include:

- Total serum IgE at baseline, day 57 (V5) and day 113 (V7)
- Allergen-specific IgE levels (birch pollen, Bet v 1) at screening visit 1 (V1) and baseline (V2)
- Allergen-specific IgE levels (Bet v 1 and other common allergens) at screening and baseline to assess sensitization status and to evaluate the relationship between response to REGN5713-5714-5715 treatment and poly/mono-sensitization
- Allergen-specific IgE levels (Bet v 1 and other common allergens) on day 57 and day 113

4.10. Other Variables

Outdoor pollen counts will be measured daily by the study site or by a vendor during the expected pollen season using a pollen sampler.

Birch Pollen Regions:

Clinical sites will be pooled into different pollen regions geographically. The pollen regions for this study include Belgium, Denmark, Germany, Canada, west-US and east-US.

CONFIDENTIAL

Page 29 of 35

Birch Pollen Season:

Local site-specific pollen count data will be used for each patient to determine the start and end of the birch pollen season. The start of the birch pollen season is defined as the first of 3 consecutive days with a pollen count of 10 grains/m³ or greater. The end of the birch pollen season is defined as the last day of the last occurrence of 3 consecutive days with a pollen count of 10 grains/m³ or greater. The peak birch pollen season is defined as the 15 consecutive days within the birch pollen season with the highest 15-day moving average pollen count.

5. STATISTICAL METHODS

For continuous variables, descriptive statistics will include the following: the number of patients reflected in the calculation (n), mean, median, Q1, Q3, standard deviation, minimum, and maximum.

For categorical or ordinal data, frequencies and percentages will be displayed for each category. Missing values at baseline will not be imputed unless otherwise specified.

5.1. Demographics and Baseline Characteristics

Demographics and Baseline Characteristics will be summarized by treatment groups and overall based on the FAS.

5.2. Medical History

Medical history will be summarized by primary SOC and PT for each treatment group and for study total based on the SAF. The table will be sorted by decreasing frequency of SOC followed by PT based on the overall incidence across treatment groups.

5.3. **Prior/Concomitant Medications/Procedures**

Number and proportion of subjects taking prior/concomitant medications, prohibited medications and will be summarized for study total based on the SAF by Anatomical Therapeutic Chemical (ATC) level 2 and ATC level 4, sorted by decreasing frequency of ATC level 2 and ATC level 4 based on the overall incidence. Subjects will be counted only once for each medication class (ATC levels 2 and 4) linked to the medication.

Number of patients taking rescue medications will be summarized by medication name based on rescue medication e-diary.

Number and proportion of patients taking prior/concomitant procedures will be summarized for study total based on the SAF, sorted by decreasing frequency of SOC and PT based on the overall incidence. Patients will be counted only once for each SOC and PT linked to the procedure.

5.4. Subject Disposition

The following summaries will be provided for each treatment group and study total (unless otherwise specified):

- The total number of screened subjects
- The total number of randomized patients: received a randomization number from IWRS
- The total number of patients in each analysis set
- The total number of patients who discontinued the study and the reasons for discontinuation (including COVID-19 related reasons)

5.5. Extent of Study Treatment Exposure and Compliance

Treatment exposure is defined as the number of study treatment administrations for each subject. Since this is a single dose study, subjects will have 1 study treatment administration, given as 3 injections sequentially on one day. Summary of number of injections will be provided. Treatment compliance is not applicable.

The duration of observation period during the study is calculated as:

(Date of the last study visit – date of the investigational product administration) +1.

Duration of observation period will be summarized for each treatment group using number of subjects, means, SD, minimums, medians and maximums.

The number (%) of subjects with observation periods will be presented by specific time periods. The time periods of interest are specified as: ≥ 1 day, ≥ 28 days, ≥ 57 days, ≥ 85 days, and ≥ 113 days.

5.6.1. Analysis of Primary Efficacy Variable

The primary analysis will focus on the comparison between the REGN5713-5714-5715 arm and placebo arm. The average CSMS during birch pollen season will be compared in subjects receiving REGN5713-5714-5715 and subjects receiving placebo using a linear mixed-effect model, with the treatment group and randomization stratification factors (serum specific birch pollen IgE levels at screening (<17.5 kUa/L, \geq 17.5 kUa/L), serum specific oak pollen IgE levels at screening (<0.7 kUa/L, \geq 0.7 kUa/L for NA) and geographical region (NA, EU)) as fixed effects and pollen region as a random effect, to account for potential differences in birch pollen seasons based on the geographical location of each pollen region. Subjects with at least 1 day of post-baseline diary record with CSMS during the birch pollen season. The least squares means (LS-means) estimate for each treatment, and LS-means for between-treatment difference with its 95% confidence interval and p-value will be provided.

The average CSMS will be calculated based on total symptom score (TNSS and TOSS, max of 18/day) and daily medication score (max of 20/day) recorded over the duration of the birch pollen season. The start and end of the birch pollen season is defined in section 4.10 for each site based on the local pollen counts.

Data after any rescue medication use will be used for the calculation of the average CSMS, but relevant prohibited medications that may have an impact on symptom measurements will result in subsequent symptoms and medication scores not be utilized in the CSMS for that subject for a specified period of time (determined by medication type). The prohibited medications will be adjudicated by study medical monitor before the database lock. A list of those relevant prohibited medication and the rules of data utilization are detailed in Table 2.

Table 2: Data Utilization for Relevant Prohibited Medications

Name of Medication	Rule of Data Utilization
Systemic steroids (oral/ IV/ IM/ intra-articular/ other)	Data will not be used after the
Type 2 Biologics	medication usage.

In additional, if a patient has major change in birch pollen exposure (e.g. travel out of country), the data will be set to missing during this major change and no imputation will be applied.

For patients with data not utilized due to prohibited medication, the following data imputation rule will be apply:

- For a patient with at least one day data to use during the birch pollen season, the worst observed score from the same patient during the birch pollen season will be used to impute the daily TNSS, TOSS and DMS in this affected period. Daily CSMS will be calculated by adding the worst daily TOSS, TNSS and DMS. Average CSMS will be calculated based on the observed scores and imputed scores.
- For a patient without any data to use during the birch pollen season, average CSMS will be imputed using the mean of average CSMS during the birch pollen season in the treatment that the patient is randomized to.

Sensitivity analysis

A sensitivity analysis is planned to assess an alternative method to impute missing data. The alternative method of calculation of average CSMS is detailed as below:

- If TOSS and/or DMS are missing on any single day with TNSS completed, it will be assumed to be 'No ocular symptom' and/or 'No rescue use' and a score of 0 will be assigned. Daily CSMS will be calculated for days with at least TNSS completed.
- The daily CSMS will be set to missing for the days that are affected by prohibited medication and/or major change in birch pollen exposure.
- The average CSMS will be calculated only based on non-missing daily CSMS during birch pollen season.

The same linear mixed-effect model will be used for the sensitivity analysis. Patients without any data during birch pollen season will not be part of the sensitivity analysis.

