# **11.2.** Justification of Sample Size

This study is powered to detect differences between REGN5713-5714-5715 and placebo on the primary endpoint of the average CSMS during birch pollen season. A sample size of 150 enrolled subjects per arm gives 90% power to detect a mean difference in average CSMS of 1.9 (30% reduction from placebo) in REGN5713-5714-5715 (mean CSMS = 4.4) and placebo (mean CSMS = 6.3), assuming a common standard deviation in CSMS of 4.5. The minimum significant difference in CSMS is 1.14, or approximately an 18% reduction from placebo. This sample size calculation assumes a 20% drop out rate (30 subjects per arm) and a two-sample t-test with two-sided alpha of 0.05. Estimates of mean and variability of the CSMS are based on pooled estimates across several field studies for grass immunotherapy, and a 30% treatment effect relative to placebo is in line with what was observed in the phase 1b POC study for REGN5713-5714-5715.

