2. INVESTIGATION PLAN

2.1. Study Design and Randomization

This is a phase 3 multi-center, randomized, double-blind, placebo-controlled, parallel group study to assess the efficacy of REGN5713-5714-5715 to reduce allergic rhinitis (nose) and conjunctivitis (eye) symptoms and the use of rescue medications during birch pollen season.

Efficacy will be evaluated by assessing the reduction of allergic nose and eye symptoms and the reduction in the use of allergy rescue medications during birch pollen season, after a single SC dose of REGN5713-5714-5715 or placebo. The incidence and severity of TEAEs, including hypersensitivity reactions and local injection site reactions, will also be assessed. Total concentration in serum and immunogenicity of REGN5713, REGN5714, and REGN5715 will be measured throughout the study.

Subjects will be randomized according to a central randomization scheme provided by interactive response Technology (IRT) to the designated study pharmacist (or qualified designee). Subjects will be randomized 1:1 as below:

- REGN5713-5714-5715
- Matching placebo

Randomization will be stratified based on the following:

- Serum specific birch pollen IgE levels at screening (<17.5 kUa/L versus ≥17.5 kUa/L)
- In North America only: Serum specific oak pollen IgE levels at screening (<0.7 kUa/L versus ≥0.7 kUa/L)
- Geographical region (North America (NA) versus Europe (EU))

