2.3. Sample Size and Power Considerations

This study is powered to detect differences between REGN5713-5714-5715 and placebo on the primary endpoint of the average CSMS during birch pollen season. A sample size of 120 subjects per arm gives 90% power to detect a mean difference in average CSMS of 1.9 (30% reduction from placebo) in REGN5713-5714-5715 (mean CSMS = 4.4) and placebo (mean CSMS = 6.3),

assuming a common standard deviation in CSMS of 4.5 with a two-sample t-test at 2-sided significance level of 0.05. Assuming 20% drop out rate during the birch pollen season, the target is to randomize 150 subjects per arm.

Estimates of mean and variability of the CSMS are based on pooled estimates across several field studies for grass sublingual immunotherapy, and a 30% treatment effect relative to placebo is in line with what was observed in the phase 1b POC study for REGN5713-5714-5715.

This planned sample size (150 subjects per arm) also gives 93% power to detect a mean difference in TNSS of 0.6 (26% reduction from placebo) in REGN5713-5714-5715 (mean TNSS=1.7) and placebo (mean TNSS=2.3), assuming a common standard deviation in TNSS of 1.5 at 2-sided alpha of 0.05 using a two-sample t-test. The assumptions of TNSS endpoint are based on effects observed in the GT-08 trial of timothy grass sublingual tablet (Dahl, 2006). With the same mean for placebo and common standard deviation from GT-08 but a 30% reduction from placebo for REGN5713-5714-5715 as observed in the phase 1b POC study, the study will have a greater power.

The sample size and power calculations were performed using nQuery Advisor 7.0

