4. ANALYSIS VARIABLES

4.1. Demographic and Baseline Characteristics

The following demographic and baseline characteristics variables will be summarized:

- Demographic variables:
 - Age at screening as a continuous variable
 - Age group (years; 18 to $<50, \ge 50$)
 - Sex (Male, Female)
 - Race (White, Black or African American, Asian, American indian or Alaska native, Native Hawaiian or other pacific islander)
 - Ethnicity (Hispanic/Latino: Yes or No)
 - Baseline Weight (kg)
 - Baseline Height (cm)
 - Region (NA, EU)
- Baseline characteristics:
 - Standard regional skin prick test (SPT) for birch (mm)
 - Serum birch pollen sIgE at screening
 - Serum oak pollen sIgE at screening (North America)
 - Serum Bet v1 sIgE at screening
 - Baseline FEV1
 - Baseline sensitization status based on sIgE or SPT (e.g. sensitization to birch and birch related allergens only, sensitization to birch, birch related allergens and any of other allergens)

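### Optional gain, not an error: the primary model uses birch sIgE only as a two-level stratum, so prognostic information within each stratum goes unused although the numeric value is collected

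*SAP*

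**What the plan says.** SAP 5.6.1 and SAP Table 1 compare average CSMS between arms with a linear mixed model. The fixed effects are treatment and the randomization factors, and pollen region is random. The randomization factors are "serum specific birch pollen IgE levels at screening" (below 17.5 kUa/L or not), oak sIgE in North America (below 0.7 kUa/L or not) and geographical region. Protocol 11.4.3.1, with the strata of 8.5, specifies the same model. No baseline measurement enters in continuous form. SAP 5.6.2 carries the model over to the secondary efficacy endpoints.

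The numeric value is available. SAP 4.1 lists "Serum birch pollen sIgE at screening" among the baseline characteristics, and inclusion criterion 4 (Protocol 7.2.1) requires at least 0.7 kUa/L, so every eligible subject should have a result.

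Continuous IgE is used elsewhere, but only for exploration. SAP 4.5.3 includes "Baseline allergen-specific IgE levels and correlation with average CSMS", and SAP 5.11 plans rank correlations and regressions of the efficacy endpoints on baseline IgE, with the log transform left open.

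The sample size (SAP 2.3) rests on an unadjusted comparison: "A sample size of 120 subjects per arm gives 90% power to detect a mean difference in average CSMS of 1.9", "assuming a common standard deviation in CSMS of 4.5 with a two-sample t-test at 2-sided significance level of 0.05". No covariate is assumed there.

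**The concern.** A two-level factor treats everyone on the same side of the cut as alike. In the lower stratum that spans 0.7 to just under 17.5 kUa/L, a 25-fold range (17.5 / 0.7 = 25). If CSMS rises or falls steadily with log sIgE, the factor removes only part of the variance that the measured value could remove, and the rest stays in the residual.

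What is at stake is the width of the confidence interval for CSMS and possibly for TNSS, TSS, TOSS and DMS, which follow in the testing hierarchy of SAP 5.6.3. In a randomized comparison, a pre-specified pre-dose covariate in a linear model leaves the treatment contrast essentially unbiased even if its functional form is imperfect. The data are already in hand.

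**Working it through.** **1. The plan's own figures.** Inputs from SAP 2.3 are a difference of 1.9, SD 4.5, two-sided alpha of 0.05 and 120 evaluable per arm; allocation is 1:1 (SAP 2.1).

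- Sample size, normal approximation: 2 × (1.960 + 1.282)² × 4.5² / 1.9² = 117.9, so 118 per arm. The exact t-test gives 119. The plan says 120.
- Standard error: 4.5 × √(2/120) = 0.581. Noncentrality: 1.9 / 0.581 = 3.27. Power from the noncentral t with 238 degrees of freedom is 90.3%.
- Minimum significant difference: 1.970 × 0.581 = 1.144, against 1.14 in Protocol 11.2.
- Dropout: 120 / (1 − 0.20) = 150 per arm, as stated.

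The stated design reproduces.

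**2. Assumptions that the documents do not supply.** These are the correlation r between log sIgE and average CSMS (taken as 0 to 0.5), the share p of subjects below 17.5 kUa/L (0.5, with 0.2 as an alternative), normality of log sIgE and a linear relation on that scale. The SD of 4.5 is read as the total SD, because SAP 2.3 attaches it to an unadjusted t-test. The mixed model is simplified to treatment and sIgE only; region, oak sIgE and pollen region are left out.

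**3. Formulas.** A two-level split keeps a fraction k = φ(c)² / [p(1 − p)] of the variance that the continuous covariate explains, where φ is the standard normal density and c is the cut on the standardized log scale. At p = 0.5, k = 2/π = 0.637. At p = 0.2, k = 0.49.

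- Residual SD with the stratum: 4.5 × √(1 − k r²)
- Residual SD with continuous log sIgE: 4.5 × √(1 − r²)
- Equivalent subjects per arm: 120 × (1 − k r²) / (1 − r²)

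Example at r = 0.3, median split: 4.5 × √(1 − 0.637 × 0.09) = 4.37 against 4.5 × √0.91 = 4.29. The variance ratio is 0.965, the standard error falls by 1.75%, and 120 / 0.965 ≈ 124.3.

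**4. Results, median split, 120 per arm.** Gains are taken before rounding.

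| r | Power, stratum | Power, continuous | Gain (points) | Fall in SE | Extra subjects per arm |
|---|---|---|---|---|---|
| 0 | 90.3% | 90.3% | 0 | 0 | 0 |
| 0.1 | 90.5% | 90.6% | 0.1 | 0.2% | 0.4 |
| 0.2 | 91.0% | 91.4% | 0.4 | 0.75% | 1.8 |
| 0.3 | 91.8% | 92.7% | 0.9 | 1.75% | 4.3 |
| 0.4 | 93.0% | 94.5% | 1.4 | 3.3% | 8.3 |
| 0.5 | 94.4% | 96.4% | 2.0 | 5.6% | 14.5 |

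With a 20/80 split the gain is 0.6 points at r = 0.2, 1.2 at 0.3 and 2.9 at 0.5. The lost degree of freedom costs less than 0.01 points.

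**5. Does it matter whether the stratum stays?** A simulation (20,000 runs, 240 subjects, treatment balanced within stratum) compared three models at r = 0.3.

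| True relation | Stratum only | Continuous only | Both |
|---|---|---|---|
| Log-linear | 91.9% | 92.7% | 92.7% |
| Step at the cut | 92.9% | 92.0% | 92.8% |

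Replacing the stratum loses power if the relation is a step. Keeping both stayed within about 0.2 points of the better single model in every simulated case.

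**6. Does the scale matter?** Yes. Under assumed skewed sIgE distributions and a log-linear truth, the untransformed value kept about 39% to 82% of the prognostic signal, against about 64% for the stratum. The log has to be fixed in advance.

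**The case against.** The strongest reply is that nothing is broken. Adjusting for the randomization factors is valid and follows the protocol, and the 90% power comes from a t-test that ignores sIgE altogether. That stands in full.

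The second reply is that the gain depends on quantities the documents do not give. That also stands: at r up to 0.3 with a median split it is under one point, and no correlation is given for TNSS, TSS, TOSS or DMS, so a benefit there is possible but not quantified.

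A reader might infer more than the documents support in four ways.

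- *The plan expects sIgE to predict CSMS, since it will correlate them.* An exploratory correlation poses a question. Protocol 3.2.1 asks whether efficacy depends on baseline IgE, which is effect modification and not the prognostic strength that yields precision.
- *Power would rise from 90.3% to as much as 93.2% with a median split.* This takes 4.5 as the SD left after the stratum. SAP 2.3 gives it for an unadjusted test, so the stratum already earns part of that rise, and the top-end gain is 2.0 points and not 2.9.
- *The cut lies near the median.* No document says so; the 64% retention is itself an assumption.
- *The change is free of any cost.* It departs from the protocol's model, and the scale and the treatment of values at the assay limits must be settled first.

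The losses from a step-shaped relation or from raw sIgE do not count against a fix that keeps the strata and specifies the log.

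**Conclusion.** The point holds as an optional efficiency gain. The primary model leaves unused any prognostic information in birch sIgE within each stratum. Under a log-linear relation, a median split, total SD 4.5 and 120 evaluable per arm, using it would add between nothing (r = 0) and about 2 power points (r = 0.5), the equivalent of 0 to about 15 subjects per arm. A 20/80 split raises the top of that range to about 2.9 points. The true figure cannot be derived from the documents. The planned analysis is neither biased nor underpowered on this account, and the sponsor could reasonably leave it as it is.

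**What to change.** Keep all randomization factors. Add log10 of the screening birch sIgE as one continuous covariate in the primary model of SAP 5.6.1 (and SAP Table 1), and in the corresponding models for TNSS, TSS, TOSS and DMS under SAP 5.6.2. State that the LLOQ/ULOQ convention of SAP 6.2 applies to the covariate. Record the change in SAP 1.2.3, which lists departures from the protocol's statistical section.

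This must be settled before unblinding; SAP section 1 allows revision until a final plan is issued ahead of data lock and code breaking. If the sponsor prefers to leave the primary model alone, the same model can be pre-specified as a supportive analysis.

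The cost is one degree of freedom, one documented departure from the protocol model and no new data.
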